3.2 Study Endpoints

3.2.1 Primary Endpoints

The primary endpoints will be:

- Time to onset, i.e. time to decrease from baseline of two points in the spontaneous NRS score,
- Peak-effect, i.e. maximal decrease from baseline in the spontaneous NRS score,
- Time to peak-effect, i.e. time to reach the peak-effect,
- Duration of effect, i.e. duration between time to onset and last timepoint for which change from baseline in the spontaneous NRS score is \geq two points.

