3.2.3 Exploratory Endpoints

The following exploratory endpoints will be evaluated:

- Change from baseline in SF-36 scores at each scheduled timepoint,
- Amount of rescue medication taken during the study,
- Time to first intake of rescue medication.

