5.2.3.2 Randomised Period

The subjects will be required to attend the CRU on several occasions during the study:

- On Day 1 in the morning, based on investigator judgement, some of the screening/run-in assessments may be redone to confirm that subjects are still compliant with the inclusion/exclusion criteria and study restrictions. If the subject is considered as stable in pain perception from the screening visit, subjects will undergo pre-dose safety

assessments and then receive the dose of IMP. After IMP dosing, subjects will undergo post-dose assessments as described in Section 18.1.

They will be instructed to continue entering their NRS score in the Actiwatch® and will be provided with a paper rescue medication diary to note their post-dose rescue medication intake (i.e. for scar pain) and NRS score immediately before intake at home (details on rescue medication are provided in Section 6.2).

They will be discharged after a minimum of two hours post-dosing.

- Out-patient visits: Subjects will be required to come back to the CRU for out-patient visits on Week 6 and Week 12.

During the randomised double-blind period (Part B), subjects will also be contacted by telephone by the CRU every day up to Day 7 (subjects might visit the CRU if required for safety purpose) and every two weeks after IMP dosing for collection of AEs, concomitant medications and compliance with pain assessments and other study requirements.

The outpatient visits and calls from Week 2 post-dosing can occur +/- three days around the scheduled date.

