6.2 Rescue Medication

Paracetamol (acetaminophen), taken orally as required, is the rescue pain medication during the randomised double-blind period (Part B) and will be provided by the CRU to the subject. It can be taken up to four times a day and should not exceed a daily dose of 4000 mg in divided doses. A single dose of rescue medication is defined as 1000 mg (two tablets).

The single paracetamol dose may be lowered to 500 mg (one tablet) if the investigator/subject feels that the dose is higher than what may be required to provide adequate analgesic effect.

For the first week, in Part B post-dose, the investigator may substitute paracetamol with co-codamol (30 mg/500 mg, maximum 4000 mg of paracetamol per day).

If the subject takes the maximum rescue medication dose of 4000 mg paracetamol per day for three consecutive days and still reports uncontrolled scar pain, the investigator should consider discontinuing the subject from the study. If uncontrolled pain elsewhere in the body were to develop, the management of this should be handled on a case-by-case basis.

The rescue medication should be swallowed whole with water and must not be broken or crushed.

The subject will be cautioned on the use of any other medication (over-the-counter or prescription containing paracetamol e.g. Lemsip®).

Rescue medication should not be taken in conjunction with other analgesic medication unless discussed with the investigator.

If rescue medication is taken, an AE and the corresponding rescue medication should be recorded in the eCRF.

The sponsor medical monitor should be contacted if further guidance is required. For questions on concomitant medications prescribed prior to study participation, the sponsor medical monitor should be contacted before the subject is included in the study.

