7.1 Adverse Events

Adverse events will be monitored and reviewed regularly by the sponsor from the time that a subject gives informed consent and throughout the study, and will be elicited by direct, nonleading questioning or by spontaneous reports.

7.1.1 *Definition of an Adverse Event*

An AE is the development of an undesirable medical condition or the deterioration of a preexisting-medical condition, whether or not considered causally related to the product. An undesirable medical condition can be symptoms (e.g. nausea, chest pain), signs (e.g. tachycardia, enlarged liver) or the abnormal results of an investigation (e.g. laboratory findings, ECG).

An AE can include an undesirable medical condition occurring at any time, even if no agent or IMP has been administered.

This definition includes events occurring from the time of the subject giving informed consent until the EoS/ED.

7.1.2 *Adverse Events Categorisation, Recording, and Follow-up*

For all AEs, sufficient information should be obtained by the investigator to determine the causality of the AE (i.e. agent or IMP administration, study procedure or other illness). The investigator is required to assess causality and record that assessment in the eCRF.

Adverse events will be classified by the investigator as mild, moderate or severe according to the following criteria:

- **Mild:** Symptoms do not alter the subject's normal functioning,
- **Moderate:** Symptoms produce some degree of impairment to function, but are not hazardous, uncomfortable or embarrassing to the subject,
- **Severe:** Symptoms definitely hazardous to well-being, significant impairment of function or incapacitation.

The relationship of an AE to agent or IMP administration will be classified by the investigator according to the following:

- **Related:** Reports including good reasons and sufficient information (e.g. plausible time sequence, dose-response relationship, pharmacology) to assume a causal relationship with agent or IMP administration in the sense that it is plausible, conceivable or likely,
- **Not related:** Reports including good reasons and sufficient information (e.g. implausible time sequence and/or attributable to concurrent disease or other drugs) to rule out a causal relationship with agent or IMP administration.

7.1.2.1 *Assessment of Expectedness*

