10.2 Rescue Medication

Details on the rescue medication are provided in Section 6.2.

Subjects will be provided with a rescue diary (paper) to record each rescue medication intake, dose, each pain increase (AE), start and stop date and time and current NRS score just before the rescue medication is taken.

If rescue medication is taken, an AE and the corresponding rescue medication should be recorded in the eCRF.

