5.8 Safety

5.8.1 *General Consideration*

All safety summaries and analyses will be based upon the Safety population. All safety data will be included in subject data listings (see listing detail conventions in Appendix A5). There will be no statistical comparison between the treatment groups for safety data.

If conversion factors are used, they should be presented either in the relevant section or a link to section 7 should be added.

5.8.2 *Extent of exposure*

In Part B, duration of exposure will be defined in weeks as:
([date of last visit attended – first IMP injection date] +1)/7.

The total dose received will be derived as followed:

- Total Dose (in U) = Number of injection site*Number of units of Dysport received,
- Total dose (in U/cm²) = Total dose / (Total painful area at day 1 pre-dose).

The following extent of exposure summaries will be presented for Part B, by treatment group and all Dysport:

- Summary of the number of injections sites,
- Summary of the volume injected (total and per site),
- Summary of the total dose received by treatment group,
- Summary of the total dose in U/cm² received by treatment group.

The following extent of exposure listings will be presented for Part A and Part B:

- Listing of exposure data (Part B only),
- Listing of subjects receiving test drugs from different batches.

5.8.3 *Adverse Events*

All adverse events (AEs) recorded in the eCRF will be coded using the latest version of MedDRA dictionary in effect within IPSEN at the time of the database lock. AEs will be classified as treatment-emergent AEs (TEAEs) according to the rules below:

- Events with start date and time on or after the date and time of IMP administration in Part B and up to End of Study (EoS) visit or Early Discontinuation (ED).
- Events whose severity worsens on or after the date and time of IMP administration in Part B and up to EoS visit or ED visit,
- Refer to appendix [A3](#) for handling of partial date. In the case where it is not possible to define an AE as treatment emergent or not, the AE will be classified by the worst case; i.e. treatment emergent.

The following summary will be provided by total dose and treatment group (i.e. by injection site dose) and all Dysport for Part B:

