- An overview table summarizing the number and percentage of subjects with at least one of the following AEs: any AE; any TEAE; any severe TEAE; treatment-related TEAE; TEAE leading to discontinuation from the study, Serious TEAE, treatment-related Serious TEAE, Serious TEAE leading to death, treatment-related Serious TEAE leading to death, Serious TEAE leading to discontinuation from the study, any Adverse Events of Special Interest (AESI).
The ranges to use for the dose will be precisely defined during the data review meeting.

The following summaries will be provided for Part B by treatment group and all Dysport groups:

- A summary of the number and percentage of subjects reporting a TEAE by treatment group, SOC and PT,
- A summary of the number and percentage of subjects reporting a TEAE by treatment group and PT,
- A summary of the number and percentage of subjects reporting a TEAE by treatment group, causality, SOC and PT,
- A summary of non-serious TEAE by treatment group, SOC and PT.

AEs summaries will be ordered in term of decreasing frequency for SOC and PT within SOC in the treatment group (Part B) and then similarly by decreasing frequency in the treatment group, and then alphabetically for SOC and PT within SOC.

AEs will be counted as follows:

- Subjects with more than one AE within a particular SOC are counted only once for that SOC. Similarly, subjects with more than one AE coding to a particular PT are counted only once for that PT;
- Subjects reporting a TEAE more than once within that SOC/ PT, the TEAE with the worst-case severity will be used in the corresponding severity summaries;

- Subjects reporting a TEAE more than once within that SOC/ PT, the TEAE with the worst-case relationship to study medication will be used in the corresponding relationship summaries;
- If the severity is missing for a TEAE, it will be considered as missing in the summary tables;
- If the causality is missing for a TEAE, it will be considered missing in the summary tables;
- The non-serious TEAEs table should include a specific row “any non-serious TEAE above x%”.

In addition, for each part, a listing with all AEs data will be listed by treatment group including non-TEAEs, Treatment-emergence status will be flagged in the listing, and AESI will also be flagged.

Deaths, Serious Adverse Events, and Other Significant Adverse Events

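### Protocol 6.2 and the end of 10.2 tie an adverse event to rescue intake, while 7.1.1 requires a new or worsened condition; read literally, unchanged scar pain enters the any-TEAE rows

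*Protocol*

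**What the plan says.** **Recording rule.** Protocol 6.2 allows oral paracetamol as needed in Part B and states: "If rescue medication is taken, an AE and the corresponding rescue medication should be recorded in the eCRF". The last sentence of 10.2 says the same. Neither sentence makes the AE conditional on the pain having worsened. According to 5.2.3.2, the intake noted in the rescue diary is intake for scar pain.

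**Definition.** Protocol 7.1.1: "An AE is the development of an undesirable medical condition or the deterioration of a preexisting-medical condition". Section 10.2, just before its closing sentence, follows that idea: subjects are to "record each rescue medication intake, dose, each pain increase (AE), start and stop date and time and current NRS score" just before intake. There the AE is the increase in pain.

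**Analysis.** SAP 5.8.3: "All adverse events (AEs) recorded in the eCRF will be coded using the latest version of MedDRA dictionary". Any event starting on or after Part B dosing, up to the end-of-study or early-discontinuation visit, is a TEAE. The overview counts subjects with "any AE; any TEAE; any severe TEAE; treatment-related TEAE" and further categories. SOC/PT, PT, causality and non-serious tables follow by treatment group. No step flags or separates AEs entered because rescue was taken. The only sorting step is the sponsor's review of AEs of special interest, which does not alter the general TEAE tables.

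**Overlap with efficacy.** The primary endpoints are built on the same symptom, for example "Peak-effect, i.e. maximal decrease from baseline in the spontaneous NRS score". Rescue use is itself an exploratory endpoint: "Amount of rescue medication taken during the study".

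**The concern.** Subjects enter with stable scar pain of NRS 4 to 8. Someone who takes paracetamol for pain at its usual level has no AE under 7.1.1 but should be given one under 6.2. Sites therefore have two recording rules that disagree for this case, and may apply either.

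Where the literal rule is applied, the TEAE count rises with insufficient analgesia. If Dysport relieves scar pain, the placebo count is raised relative to Dysport, and a real excess of other events on Dysport can look smaller or vanish in the summary row. The same intake would then be read once as weak analgesia, in the rescue endpoint, and once as poor tolerability, in the TEAE overview. Safety and tolerability is a secondary objective, and TEAE incidence by arm is one of its main displays.

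**Working it through.** **1. The route from intake to table**

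| Step | Source | Unchanged scar pain, rescue taken |
|---|---|---|
| Is it an AE by definition? | Protocol 7.1.1 | No: neither new nor worse |
| Is it an AE by the diary instruction? | Protocol 10.2, diary sentence | No: no pain increase |
| Is it an AE by the rescue rule? | Protocol 6.2; 10.2, last sentence | Yes: rescue was taken |
| Is it a TEAE once recorded? | SAP 5.8.3 | Yes: starts after dosing |
| Is it separated in the overview? | SAP 5.8.3 | No |

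If the pain has worsened, all the recording rules agree and the event belongs in the tables. The conflict is confined to rescue taken for pain that is not worse.

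**2. Arm sizes**

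The inputs are about 24 subjects (Protocol synopsis) and the ratio 3:1:3:1:3:1 (Protocol 3.4.1.2). Each dose gets 24 × 3/12 = 6 subjects. Each matching placebo gets 24 × 1/12 = 2, so pooled placebo is 3 × 2 = 6. This reproduces the stated six per arm.

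One subject is 1/6 = 16.7 points of an arm's incidence, two are 33.3 points, and one in the all-Dysport column is 1/18 = 5.6 points. A rescue user moves the any-TEAE row by this step only if that subject has no other TEAE; otherwise the row does not change.

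**3. Illustration with assumed rates**

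Let s be the risk of any other TEAE and q the risk of an AE recorded only because of rescue, taken as independent. Then P(any TEAE) = 1 − (1 − s)(1 − q). The documents give neither s nor q, so every value of s and q below is an assumption, chosen to show a range.

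| s placebo / Dysport | q placebo / Dysport | Any TEAE, placebo | Any TEAE, Dysport | Displayed difference (true difference) |
|---|---|---|---|---|
| 20% / 20% | 1/6 / 0 | 1 − 0.8 × 5/6 = 33.3% | 20.0% | −13.3 (0) |
| 20% / 20% | 4/6 / 2/6 | 1 − 0.8 × 2/6 = 73.3% | 1 − 0.8 × 4/6 = 46.7% | −26.7 (0) |
| 20% / 40% | 1/6 / 0 | 33.3% | 40.0% | +6.7 (+20) |
| 20% / 40% | 2/6 / 1/6 | 1 − 0.8 × 4/6 = 46.7% | 1 − 0.6 × 5/6 = 50.0% | +3.3 (+20) |
| 20% / 40% | 4/6 / 2/6 | 73.3% | 1 − 0.6 × 4/6 = 60.0% | −13.3 (+20) |
| 20% / 40% | 3/6 / 3/6 | 1 − 0.8 × 0.5 = 60.0% | 1 − 0.6 × 0.5 = 70.0% | +10.0 (+20) |

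Differences are Dysport minus placebo, in percentage points. Even equal rescue use shrinks a true excess, because some subjects who would have counted for another event are already counted. The rows with 4/6 show the mechanism at heavy use; the SAP's remark that rescue use was low makes them unlikely here.

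**The case against.** The strongest reply is that 10.2 shows what was meant: the AE is the pain increase. Subjects must be on stable analgesia, so rescue on top of it will often mean that pain has worsened, which is a valid AE. That stands for worsened pain. It does not remove the closing sentence of 10.2 or the rule in 6.2, neither of which carries that condition.

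Other points also stand and limit the finding:

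- Both sections say should, not must. A reader might infer that every intake is bound to become a TEAE; the wording does not go that far. Uneven compliance, however, would make AE capture inconsistent.
- Safety is descriptive, with no between-group test. SOC/PT tables, the full AE listing, the rescue listing and the flags on NRS values for rescue days let a reader cross-check about 24 subjects by hand. The summary rows are where the events merge. Treatment-related rows depend on the investigator's causality judgement.
- SAP 2.6 describes rescue use as low, to be confirmed at the blind data review, and gives no count. A reader might infer one or two affected subjects per arm; no such figure is in the documents, and it could be none. With 4 to 10 intradermal injections each, and local reactions listed as known effects in Protocol 1.8, a rescue user may well have another TEAE already.
- A reader might also infer that painful injections in one arm would distort the tables in the same way. They would not: injection-site pain is genuine tolerability information and should be counted.
- The diary score is current pain at intake (Protocol 10.2). The SAP 5.1.3 baseline is a mean of pre-dose ratings from Day −7, each covering 12 hours (Protocol 9.1.3). These are not like with like, and SAP 2.6 already notes difficulty in linking NRS scores to rescue. A fixed numerical cut-off is therefore not a sound way to classify events.

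**Conclusion.** The two recording rules contradict each other for rescue taken without worsening, and the SAP has no step that separates the resulting events. Taken literally, summary rows such as any TEAE partly reflect lack of analgesia. The size cannot be determined from the documents. Its upper step is 16.7 points per affected subject in an arm of six, conditional on that subject having no other TEAE; the illustrated shifts rest wholly on assumed rates and independence.

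A reader might conclude that TEAE differences between arms cannot be read as tolerability at all. The documents do not support that. Severe, serious and treatment-related TEAEs, AEs of special interest, vital signs and the scar examination are also reported, and no primary endpoint or NRS analysis is affected. The case for changing the plan is that the ambiguity is avoidable at little cost.

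**What to change.** **Protocol.** Reconcile 6.2 and the last sentence of 10.2 with 7.1.1, so that the AE recorded is the pain increase and not the intake itself. All intakes remain in the rescue diary and the medication record. This concerns recording only; nothing about how rescue is used changes.

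**SAP 5.8.3.** Keep every existing table and listing. Add a TEAE overview and a SOC/PT summary that leave out scar-pain AEs recorded only because rescue was taken, and show those events in their own row. Injection-site pain and scar pain that worsened stay in.

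**Identification.** Classify the events at the blind data review, before unblinding, from the AE term, the investigator's assessment and the rescue diary. Do not apply a mechanical cut-off of the current pre-intake NRS against the mean 12-hour baseline.

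**Cost.** A change of wording in two protocol sections, one supplementary safety display (the overview and its SOC/PT summary), and a blinded judgement on what should be a few events. No safety data are lost, because the existing displays remain.

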6.3 Concomitant Medications

Any prior or concomitant medication given to a subject 30 days prior to dosing and during the study will be reported in the eCRF. Dose and trade name will be recorded. The dose of the concomitant medications taken during the randomised double-blind period should be kept constant, where possible, until the EoS.

All medications not prohibited by the protocol and considered necessary for the subject's welfare may be administered and/or continued under the supervision of the investigator.

Only analgesia medication which has been stable during the previous month prior to entry into the study will be allowed.

6.4 Subject Compliance Monitoring

The investigator will be responsible for monitoring subject compliance.

7 SAFETY ASSESSMENTS

The following safety parameters will be collected and reviewed during the study at specific timepoints as described in the study schedule of assessments in Section 18.1:

- AEs,
- Concomitant medications,
- Medical and surgical history,
- Physical examination (including height, body weight, body temperature, examination of the scar at the injection sites),
- Vital signs (including heart rate (HR), and diastolic (DBP) and systolic blood pressures (SBP)).

Further routine medical assessments or any additional safety procedures may be performed during the study, if warranted and agreed upon between the sponsor and the investigator, or when clinically indicated.

The investigator will be responsible for a clinical assessment of the study participants during the whole participation of the subjects in the study, from informed consent up to discharge from the study, and for the set up of a discharge plan if needed.

Every effort should be made to ensure that all safety evaluations are completed by the same individual who made the initial baseline determination.

The sponsor medical monitor and the GPS physician will monitor safety data throughout the course of the study.

Any new clinically significant finding should be recorded as an AE from the time informed consent is given.

7.1 Adverse Events

Adverse events will be monitored and reviewed regularly by the sponsor from the time that a subject gives informed consent and throughout the study, and will be elicited by direct, nonleading questioning or by spontaneous reports.

7.1.1 *Definition of an Adverse Event*

An AE is the development of an undesirable medical condition or the deterioration of a preexisting-medical condition, whether or not considered causally related to the product. An undesirable medical condition can be symptoms (e.g. nausea, chest pain), signs (e.g. tachycardia, enlarged liver) or the abnormal results of an investigation (e.g. laboratory findings, ECG).

An AE can include an undesirable medical condition occurring at any time, even if no agent or IMP has been administered.

This definition includes events occurring from the time of the subject giving informed consent until the EoS/ED.

7.1.2 *Adverse Events Categorisation, Recording, and Follow-up*

For all AEs, sufficient information should be obtained by the investigator to determine the causality of the AE (i.e. agent or IMP administration, study procedure or other illness). The investigator is required to assess causality and record that assessment in the eCRF.

Adverse events will be classified by the investigator as mild, moderate or severe according to the following criteria:

- **Mild:** Symptoms do not alter the subject's normal functioning,
- **Moderate:** Symptoms produce some degree of impairment to function, but are not hazardous, uncomfortable or embarrassing to the subject,
- **Severe:** Symptoms definitely hazardous to well-being, significant impairment of function or incapacitation.

The relationship of an AE to agent or IMP administration will be classified by the investigator according to the following:

- **Related:** Reports including good reasons and sufficient information (e.g. plausible time sequence, dose-response relationship, pharmacology) to assume a causal relationship with agent or IMP administration in the sense that it is plausible, conceivable or likely,
- **Not related:** Reports including good reasons and sufficient information (e.g. implausible time sequence and/or attributable to concurrent disease or other drugs) to rule out a causal relationship with agent or IMP administration.

7.1.2.1 *Assessment of Expectedness*

The expectedness of an AE shall be determined by the sponsor according to the latest approved version of the Dysport Investigator's brochure (IB) and the lidocaine SmPC in the UK (Marketing authorisation number **CCI** [REDACTED]).

7.1.2.2 *Follow-Up of Adverse Events*

Any AEs already recorded and designated as "continuing" should be reviewed at each subsequent assessment.

If an AE is still present at the end of the study, reasonable follow-up clinical monitoring (and up to 30 days after the end of the study) should be managed by the investigator or any appropriate physician until the event or its sequelae resolves or stabilises at an acceptable level, as judged by the investigator. The frequency of follow-up evaluation is left to the investigator's discretion.

7.1.2.3 *Reporting of Adverse Events*

Any AE considered related to agent or IMP administration that the investigator becomes aware of after completion of the EoS/ED visit must be reported to the sponsor and will be recorded in the corresponding database.

7.1.3 *Serious Adverse Event Assessment and Reporting to Sponsor*

The investigator must pursue and obtain adequate information to determine the outcome of the AE and to assess whether it meets criteria for classification as an SAE requiring immediate notification to the GPS department of the sponsor.

An SAE is any AE that:

- Results in death,
- Is life-threatening, that is any event that places the subject at immediate risk of death from the event as it occurs. It does not include an event that, had it occurred in a more severe form, might have caused death,
- Results in in-patient hospitalisation or prolongation of existing hospitalisation, excluding admission for social or administrative reasons,

- Hospitalisation is defined as any in-patient admission (even if less than 24 hours). For chronic or long term in-patients, in-patient admission also includes transfer within the hospital to an acute/intensive care in-patient unit,
- Prolongation of hospitalisation is defined as any extension of an in-patient hospitalisation beyond the stay anticipated/required in relation to the original reason for the initial admission, as determined by the investigator or treating physician. For protocol-specified hospitalisation in clinical studies, prolongation is defined as any extension beyond the length of stay described in the protocol. Prolongation in the absence of a precipitating, treatment emergent, clinical AE (i.e. not associated with the development of a new AE or worsening of a pre-existing condition) may meet criteria for “seriousness” but is not an adverse experience and thus is not subject to immediate reporting to the sponsor,
- Preplanned or elective treatments/surgical procedures should be noted in the subject's screening documentation. Hospitalisation for a preplanned or elective treatment/surgical procedure should not be reported as an SAE unless there are complications or sequelae which meet the criteria for seriousness described above,
- Results in a persistent or significant disability/incapacity, where disability is a substantial disruption of a person's ability to conduct normal life functions,
- Results in congenital anomaly/birth defect in the offspring of a subject who received the agent or IMP,
- Is an important medical event that may not result in death, be life-threatening, or require hospitalisation when, based upon appropriate medical judgement, may jeopardise the subject and may require medical or surgical intervention to prevent one of the outcomes listed in this definition. Examples of such medical events include allergic bronchospasm requiring intensive treatment in an emergency room or at home, blood dyscrasias or convulsions that do not result in in-patient hospitalisation, or the development of drug dependency or drug abuse.

All SAEs regardless of treatment group or suspected relationship to agent or IMP must be reported immediately (**within 24 hours** of the investigator's knowledge of the event) using the fax number specified on the front page of the current document.

Any appropriate means of notification may be used. If the immediate report is submitted by telephone, this must be followed by detailed written reports using the SAE report form.

The following information is the minimum that must be provided to the sponsor:

- Study number,
- CRU,
- Subject number,
- AE,
- Causality,
- Investigator's name and contact details.

The additional information included in the SAE form must be provided to the sponsor or representative as soon as it is available. The investigator should always provide an assessment of causality for each event reported to the sponsor. Upon receipt of the initial report, the sponsor will ask for the investigator's causality assessment if it was not provided with the initial report. The investigator should report a diagnosis or a syndrome rather than individual signs or symptoms. The investigator should also try to separate a primary AE considered as the foremost untoward medical occurrence from secondary AEs which occurred as complications.

